10.7. Appendix 7: Kidney Safety: Monitoring Guidelines

10.7.1. Laboratory Assessment of Change in Kidney Function and Detection of Kidney Injury

Standard kidney safety monitoring requires assessment of baseline and postbaseline serum creatinine (Scr measurement to estimate glomerular filtration rate [Scr-based eGFR] or creatinine clearance [eCrCl]). Baseline and postbaseline serum Scys makes it feasible to distinguish AKI from other causes of Scr increase. If Scr increase is confirmed after baseline, then reflex measurement of Scys is indicated to estimate the combined Scr-Scys eGFR calculation (for adults only).

Regardless of whether kidney function monitoring tests are required as a routine safety monitoring procedure in the study, if the investigator or sponsor deems it necessary to further assess kidney safety and quantify kidney function, then these test results should be managed and followed per standard of care.

10.7.2. Age-Specific Kidney Function Calculation Recommendations

10.7.2.1. Adults (18 Years and Above)—2021 CKD-EPI Equations

2021 CKD-EPI, Scr Only	Scr (mg/dL)	Scys (mg/L)	Recommended eGFR Equation
Female	if ≤ 0.7	N/A	$eGFR = 143 \times (Scr/0.7)^{-0.241} \times (0.9938)^{Age}$
Female	if > 0.7	N/A	$eGFR = 143 \times (Scr/0.7)^{-1.200} \times (0.9938)^{Age}$
Male	if ≤ 0.9	N/A	$eGFR = 142 \times (Scr/0.9)^{-0.302} \times (0.9938)^{Age}$
Male	if > 0.9	N/A	$eGFR = 142 \times (Scr/0.9)^{-1.200} \times (0.9938)^{Age}$
2021 CKD-EPI, Scr-Scys Combined	Scr (mg/dL)	Scys (mg/L)	Recommended eGFR Equation
Female	if ≤ 0.7	if ≤ 0.8	$eGFR = 130 \times (Scr/0.7)^{-0.219} \times (Scys/0.8)^{-0.323} \times (0.9961)^{Age}$
Female	if ≤ 0.7	if > 0.8	$eGFR = 130 \times (Scr/0.7)^{-0.219} \times (Scys/0.8)^{-0.778} \times (0.9961)^{Age}$
Female	if > 0.7	if ≤ 0.8	$eGFR = 130 \times (Scr/0.7)^{-0.544} \times (Scys/0.8)^{-0.323} \times (0.9961)^{Age}$
Female	if > 0.7	if > 0.8	$eGFR = 130 \times (Scr/0.7)^{-0.544} \times (Scys/0.8)^{-0.778} \times (0.9961)^{Age}$
Male	if ≤ 0.9	if ≤ 0.8	$eGFR = 135 \times (Scr/0.9)^{-0.144} \times (Scys/0.8)^{-0.323} \times (0.9961)^{Age}$
Male	if ≤ 0.9	if > 0.8	$eGFR = 135 \times (Scr/0.9)^{-0.144} \times (Scys/0.8)^{-0.778} \times (0.9961)^{Age}$
Male	if > 0.9	if ≤ 0.8	$eGFR = 135 \times (Scr/0.9)^{-0.544} \times (Scys/0.8)^{-0.323} \times (0.9961)^{Age}$
Male	if > 0.9	if > 0.8	$eGFR = 135 \times (Scr/0.9)^{-0.544} \times (Scys/0.8)^{-0.778} \times (0.9961)^{Age}$

Inker LA et al. N Engl J Med. 2021;385:1737-49.

10.7.3. Adverse Event Grading for Kidney Safety Laboratory Abnormalities

AE grading for decline in kidney function (ie, eGFR or eCrCl) will be according to CTCAE criteria.

10.8. Appendix 8: ECG Findings of Potential Clinical Concern

ECG Findings That May Qualify as AEs

Marked sinus bradycardia (rate <40 bpm) lasting minutes.New PR interval prolongation >280 ms.New prolongation of QTcF to >480 ms (absolute) or by ≥ 60 ms from baseline.New-onset atrial flutter or fibrillation, with controlled ventricular response rate: ie, rate <120 bpm.New-onset type I second-degree- (Wenckebach) AV block of >30 seconds' duration.Frequent PVCs, triplets, or short intervals (<30 seconds) of consecutive ventricular complexes.
ECG Findings That May Qualify as SAEs

QTcF prolongation >500 ms.New ST-T changes suggestive of myocardial ischemia.New-onset LBBB (QRS complex >120 ms).New-onset right bundle branch block (QRS complex >120 ms).Symptomatic bradycardia.Asystole:
In awake, symptom-free participants in sinus rhythm, with documented periods of asystole ≥ 3.0 seconds or any escape rate <40 bpm, or with an escape rhythm that is below the AV node.In awake, symptom-free participants with atrial fibrillation and bradycardia with 1 or more pauses of at least 5 seconds or longer.Atrial flutter or fibrillation, with rapid ventricular response rate: rapid = rate >120 bpm.Sustained supraventricular tachycardia (rate >120 bpm) ("sustained" = short duration with relevant symptoms or lasting >1 minute).Ventricular rhythms >30 seconds' duration, including idioventricular rhythm (HR <40 bpm), accelerated idioventricular rhythm (HR >40 bpm to <100 bpm), and

monomorphic/polymorphic ventricular tachycardia (HR >100 bpm [such as torsades de pointes]).

- Type II second-degree (Mobitz II) AV block.
- Complete (third-degree) heart block.

ECG Findings That Qualify as SAEs

- Change in pattern suggestive of new myocardial infarction.
- Sustained ventricular tachyarrhythmias (>30 seconds' duration).
- Second- or third-degree AV block requiring pacemaker placement.
- Asystolic pauses requiring pacemaker placement.
- Atrial flutter or fibrillation with rapid ventricular response requiring cardioversion.
- Ventricular fibrillation/flutter.
- At the discretion of the investigator, any arrhythmia classified as an adverse experience.

The enumerated list of major events of potential clinical concern are recommended as “alerts” or notifications from the core ECG laboratory to the investigator and Pfizer study team, and not to be considered as all-inclusive of what to be reported as AEs/SAEs.

10.9. Appendix 9: Prohibited Concomitant Medications That May Result in DDI

The prohibited concomitant medications listed below should not be taken with PF-07284890 throughout the conduct of the study, and some have required washout period as listed in the table.

The Pfizer study team is to be notified of any prohibited medications taken during the study. After consulting with the sponsor, the investigator will make a judgment on the ongoing participation of any participant with prohibited medication use during the study.

This list of drugs prohibited for potential DDI concerns with the IMP may be revised during the course of the study with written notification from sponsor, to include or exclude specific drugs or drug categories for various reasons (eg, emerging DDI results for the IMP, availability of new information in literature on the DDI potential of other drugs).

This is not an all-inclusive list. Site staff should consult with the sponsor or designee with any questions regarding potential DDI.

Investigators should consult the product label for any other medication used during the study for information regarding medication that is prohibited for concomitant use.

Table 10. Prohibited Concomitant Medications that May Result in DDI

Drug Category	Drugs	Guidance	Required Washout Period Prior to the First Dose of PF-07284890
CCI			
Proton pump inhibitors	dexlansoprazole esomeprazole ilaprazole ^a lansoprazole omeprazole pantoprazole rabeprazole	Prohibited	7 days
PF-07799933 as Perpetrator of DDI			
CYP3A substrates that have a narrow therapeutic index (NTI)	alfentanil amiodarone argatroban astemizole ^a carbamazepine cisapride ^a cyclosporine dihydroergotamine	Prohibited	N/A

PFIZER CONFIDENTIAL

Table 10. Prohibited Concomitant Medications that May Result in DDI

Drug Category	Drugs	Guidance	Required Washout Period Prior to the First Dose of PF-07284890
	ergotamine fentanyl (excluding transdermal patch) pimozide quinidine sirolimus tacrolimus terfenadine		

a. Not approved in the US as of October 2020, but may be available in other countries including Korea, China and Mexico.

10.10. Appendix 10: Abbreviations

The following is a list of abbreviations that may be used in the protocol.

Abbreviation	Term
%CV	percent coefficient of variation
Abs	absolute
ADL	activity/activities of daily living
AE	adverse event
AESI	adverse event of special interest
AKI	acute kidney injury
ALP	alkaline phosphatase
ALT	alanine aminotransferase
ANC	absolute neutrophil count
aPTT	activated partial thromboplastin time
AST	aspartate aminotransferase
ATC	anaplastic thyroid cancer
AUC	area under the plasma concentration-time curve
AUC _{24hr}	area under the plasma concentration-time curve from time zero to 24 hours
AUC _{inf}	area under the plasma concentration-time curve from time zero extrapolated to infinity
AUC _{last}	area under the plasma concentration-time profile from time zero to the time of the last quantifiable concentration (Clast).
AUC _{tau}	area under the plasma concentration-time curve from time zero to tau (ie, over the dosing interval)
AV	atrioventricular
AxMP	auxiliary medicinal product
BBS	Biospecimen Banking System
BCRP	breast cancer resistance protein
BID	twice daily
BLRM	Bayesian Logistic Regression Model
BMI	body mass index
BP	blood pressure
bpm	beats per minute
BRAF	B-type Raf proto-oncogene
BRAFi	B-type Raf proto-oncogene inhibitor
BUN	blood urea nitrogen
C1D1	Cycle 1 Day 1
C1D15	Cycle 1 Day 15
CFR	Code of Federal Regulations
CI	confidence interval
CIOMS	Council for International Organizations of Medical Sciences
CK	creatine kinase
CKD-EPI	chronic kidney disease epidemiology

PFIZER CONFIDENTIAL

Abbreviation	Term
CL/F	apparent clearance
C_{last}	the last quantifiable concentration
C_{max}	maximum observed concentration
CNS	central nervous system
CO ₂	carbon dioxide (bicarbonate)
COVID-19	coronavirus disease 2019
Cp	plasma concentration
CR	complete response
CRC	colorectal cancer
CRF	case report form
CRO	contract research organization
CRU	clinical research unit
CSR	Clinical Study Report
CT	clinical trial
CTCAE	Common Terminology Criteria for Adverse Events
CTIS	Clinical Trial Information System
CTMS	Clinical Trial Management System
C_{trough}	pre-dose plasma concentration
CYP	cytochrome P450
DCT	data collection tool
DDI	drug-drug interaction
DICI	drug-induced creatinine increase
DIKI	drug-induced kidney injury
DILI	drug-induced liver injury
DLT	dose-limiting toxicity
DME	drug metabolizing enzyme
DNA	deoxyribonucleic acid
DoR	duration of response
EC	ethics committee
ECC	emergency contact card
ECG	electrocardiogram or electrocardiography
ECOG	Eastern Cooperative Oncology Group
eCrCl	estimated creatinine clearance
eCRF	electronic case report form
EDB	exposure during breastfeeding
E-DMC	External Data Monitoring Committee
EDP	exposure during pregnancy
eGFR	estimated glomerular filtration rate
eSAE	electronic serious adverse event
EU	European Union
EudraCT	European Union Drug Regulating Authorities Clinical Trials (European Clinical Trials Database)
FIH	first in human

Abbreviation	Term
FSH	follicle-stimulating hormone
HR	heart rate
GCP	Good Clinical Practice
GGT	gamma-glutamyl transferase
GI	gastrointestinal
GLP	Good Laboratory Practice
HBcAb	hepatitis B core antibody
HBsAg	hepatitis B surface antigen
Hct	hematocrit
HCVAb	hepatitis C antibody
hERG	human ether-à-go-go-related gene
Hgb	hemoglobin
HIV	human immunodeficiency virus
HNSTD	highest non-severely toxic dose
HR	heart rate
HRT	hormone replacement therapy
HV	healthy volunteer
IB	Investigator's Brochure
IC ₅₀	half-maximal inhibitory concentration
IC ₉₀	90% of the maximum inhibition concentration
ICD	informed consent document
ICH	International Council for Harmonisation of Technical Requirements for Pharmaceuticals for Human Use
ID	identification
IMP	investigational medicinal product
IND	Investigational New Drug
INR	international normalized ratio
IPAL	Investigational Product Accountability Log
IPM	investigational product manual
IQMP	Integrated Quality Management Plan
IRB	Institutional Review Board
IV	intravenous(ly)
K ₂ -EDTA	dipotassium ethylenediaminetetraacetic acid
K _{el}	terminal phase rate constant
LBBB	left bundle branch block
LFT	liver function test
MAPK	mitogen-activated protein kinase
MCH	mean corpuscular hemoglobin
MCHC	mean corpuscular hemoglobin concentration
MCV	mean corpuscular volume
MEK	mitogen/extracellular signal regulated kinase
NHP	nonhuman primate
MOE	margin of exposure

[figure not shown]
Abbreviation	Term
MQI	medically qualified individual
MTD	maximum tolerated dose
N/A	not applicable
ND	no data
NIMP	noninvestigational medicinal product
NOAEL	no-observed-adverse-effect level
NSCLC	non-small cell lung cancer
NTI	narrow therapeutic index
OCT	optical coherence tomography
PCR	polymerase chain reaction
PCRU	Pfizer Clinical Research Unit
PD	pharmacodynamic(s)
PE	physical examination
PFS	progression-free survival
PI	principal investigator
PK	pharmacokinetic(s)
PPI	proton pump inhibitor
PR	pulse rate
PS	performance status
PSSA	Pfizer's Serious Adverse Event Submission Assistant
PT	prothrombin time
PTC	papillary thyroid cancer
PVC	premature ventricular contraction/complex
QD	once daily
QRS	time from ECG Q wave to the end of the S wave corresponding to ventricle depolarization
QTc	corrected QT interval
QTcF	QTc corrected using Fridericia's formula
qual	qualitative
R _{AUC}	accumulation ratio based on AUC
RBC	red blood cell
R _{C_{max}}	accumulation ratio based on C _{max}
RDE	recommended dose for expansion
RNA	ribonucleic acid
RPED	retinal pigment epithelial detachment
RR	respiratory rate
RT-PCR	reverse transcriptase-polymerase chain reaction
RVO	retinal vein occlusion
SAE	serious adverse event
SAP	Statistical Analysis Plan
SARS-CoV-2	severe acute respiratory syndrome coronavirus 2
SCr	serum creatinine
Scys	serum cystatin C

Abbreviation	Term
SEER	Surveillance, Epidemiology, and End Results
SoA	schedule of activities
SOP	standard operating procedure
SRS	stereotactic radiosurgery
SRSD	Single Reference Safety Document
STD ₁₀	severely toxic dose in 10% of the animals
SUSAR	Suspected Unexpected Serious Adverse Reaction
t _½	terminal elimination half-life
T bili	total bilirubin
TEAE	treatment-emergent adverse event
THC	tetrahydrocannabinol
TK	toxicokinetics
T _{max}	time to reach C _{max}
UACR	urine albumin/creatinine ratio
CCI	
ULN	upper limit of normal
US	United States
UTI	urinary tract infection
UVB	ultraviolet B
V _z /F	apparent volume of distribution for extravascular dosing
WBC	white blood cell
WOCBP	woman/women of childbearing potential
WBRT	whole-brain radiotherapy

1. VERSION HISTORY

Table 1. Summary of Changes

Version/ Date	Associated Protocol Amendment	Rationale	Specific Changes
1 17 May 2022	Original 06 Apr 2022	N/A	N/A

2. INTRODUCTION

PF-07284890 (also known as ARRY-461) is a potent, selective, highly brain-penetrant small-molecule inhibitor of BRAF V600 mutations that is currently being developed for the treatment of BRAF V600-mutant solid tumors with or without brain involvement.

The purpose of the study is to evaluate the effect of a low-fat and high-fat meal on the relative bioavailability of PF-07284890 following single dose oral administration of PF-07284890 using 2 of the 100 mg PF-07284890 tablets currently used in the first-in-patient study C4471001 (200 mg per single dose). Results from the study will be used to inform food instructions for patients in PF-07284890 first-in-patient study C4471001, Phase 1b.

This SAP provides the detailed methodology for summary and statistical analyses of the data collected in Study C4471002.

2.1. Modifications to the Analysis Plan Described in the Protocol

Not applicable.

2.2. Study Objectives, Endpoints, and Estimands

[figure not shown]
The following are the objectives and endpoints in this study. Estimand framework is not applied to this phase 1 study.

Objectives	Endpoints
Primary:	Primary:

 • To evaluate the effect of a low-fat meal on the exposures of PF-07284890 following a single oral 200-mg dose • To evaluate the effect of a high-fat meal on the exposures of PF-07284890 following a single oral 200-mg dose 	
 • Comparison of low-fat meal with fasted PK: The ratio of AUC_{last}, AUC_{inf} (if data permit) and C_{max} of PF-07284890 • Comparison of high-fat meal with fasted PK: The ratio of AUC_{last}, AUC_{inf} (if data permit) and C_{max} of PF-07284890
Secondary:	Secondary:

 • To characterize the pharmacokinetic parameters of PF-07284890 following a single oral 200-mg dose 	
 • T_{max}, $t_{1/2}$, CL/F and V_z/F (if data permit).

 • To evaluate the safety and tolerability of PF-07284890 in healthy participants 	
 • Assessment of TEAEs, clinical laboratory abnormalities, vital signs, and 12-lead ECGs.
CC1 	

2.3. Study Design

This is a Phase 1, open-label, randomized, single dose, 3-treatment, 2-sequence, 3-period crossover study to evaluate the effect of a low-fat and high-fat meal on the relative bioavailability of PF-07284890 following a single oral dose of PF-07284890 using two 100-mg tablets of PF-07284890 in healthy adult participants, males and females of non-childbearing potential. The study will consist of 3 treatments: a single oral dose of 200 mg PF-07284890 (2 × 100 mg tablets) under fasted conditions (Treatment A, Reference), a single oral dose of 200 mg PF-07284890 (2 × 100 mg tablets) under low-fat meal fed conditions (Treatment B, Test 1), and a single oral dose of 200 mg PF-07284890 (2 × 100 mg tablets) under high-fat meal fed conditions (Treatment C, Test 2).

Approximately 12 healthy participants will be randomly assigned to study intervention such that approximately 6 participants will be enrolled to each sequence. Participants who discontinue from the study for non-safety reasons may be replaced at the sponsor's discretion in collaboration with the investigator.

Figure 1. C4471002 Study Schema

3. ENDPOINTS AND BASELINE VARIABLES: DEFINITIONS AND CONVENTIONS

3.1. Primary Endpoints

The primary endpoints are the ratios of AUC_{last} , AUC_{inf} (if data permit) and C_{max} of PF-07284890 under the fed conditions (low-fat meal or high-fat meal), relative to the PK parameters under the fasted conditions.

3.2. Secondary Endpoints

The secondary endpoints are the plasma PK parameters of PF-07284890, which will be derived (as data permit) from the concentration-time data using standard noncompartmental methods of analysis as outlined in Table 2. *Actual PK sampling times will be used in the derivation of PF-07284890 PK parameters when available. In the case that actual PK sampling times are not available, nominal PK sampling time will be used in the derivation of PK parameters.*

Table 2. Plasma PF-07284890 PK Parameters Definitions

Parameter	Definition	Method of Determination
AUC_{inf}^*	Area under the plasma concentration-time curve from time zero extrapolated to infinity	$AUC_{last} + (C_{last}^* / k_{el})$, where C_{last}^* is the predicted plasma concentration at the last quantifiable time point from the log-linear regression analysis
AUC_{last}	Area under the plasma concentration-time profile from time zero to the time of the last quantifiable concentration (C_{last}).	Linear/Log trapezoidal method.
C_{max}	Maximum observed plasma concentration	Observed directly from data
T_{max}	Time to reach C_{max}	Observed directly from data as time of first occurrence
$t_{1/2}^*$	Terminal elimination half-life	$\log_2(2) / k_{el}$, where k_{el} is the terminal phase rate constant calculated by a linear regression of the loglinear concentration-time curve. Only those data points judged to describe the terminal loglinear decline will be used in the regression.
CL/F^*	Apparent clearance	$Dose/AUC_{inf}$
V_z/F^*	Apparent volume of distribution for extravascular dosing	$Dose/(AUC_{inf} \cdot k_{el})$

*If data permit.

Safety data are also considered as secondary endpoints and are discussed in Section 3.5.

CCI

3.4. Baseline Variables

Baseline characteristics will be collected according to the schedule of activities (SoA) as specified in the protocol.

3.5. Safety Endpoints

The following data are considered in standard safety summaries (see protocol for collection days, baseline assessment, and list of parameters):

- adverse events (AE)

- laboratory data
- vital signs data
- electrocardiogram (ECG) results

3.5.1. Adverse Events

Any events occurring following start of treatment will be considered as treatment emergent adverse event (TEAE). Events that occur in a non-treatment period (ie washout or follow-up period) within the lag time of 28 days will be counted as treatment emergent and attributed to the previous treatment taken. Similarly, the time period for collecting AEs (“active collection period”) for each participant begins from the time the participant provides informed consent.

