- a. Screening will be performed within 28 days prior to the first dose of PF-07284890.
- b. Period 2 will begin on Study Period 1, Day 5 (referred to as Period 2, Day -1). Period 3 will begin on Study Period 2, Day 5 (referred to as Period 3, Day -1). Day -1 activities will be performed only for Day -1 of Period 1 unless otherwise indicated.
- c. Participants will be admitted to the CRU at least 12 hours prior to PF-07284890 dose on Day 1 of Period 1. Participants will be discharged on Day 4 of Study Period 3 following completion of all assessments.
- d. Medical history will include a history of prior illegal drug, alcohol, and tobacco use, as well as blood donation within prior 60 days. Medical history will be recorded at screening and updated on Day -1 of Period 1.
- e. Demographics will include participant race, ethnicity, age, and gender during the screening visit.
- f. Physical examination will be performed by trained medical personnel at the investigator site at screening or Day -1 of Period 1 only (height and weight must be obtained at screening to obtain BMI for eligibility criteria). A brief PE will be performed on Day -1 of Periods 2 and 3, and may be performed at other designated time points at the discretion of the investigator.
- g. Safety laboratory assessments including urinalysis, hematology, chemistry and coagulation will be performed at the indicated time-points, including Day -1 and Day 2 at 24 hours post-dose of all 3 Periods. All the safety laboratory samples must be collected following at least a 4-hour fast. Additional safety laboratory assessments may be performed at any time at the discretion of the investigator.
- h. For postmenopausal (amenorrheic for at least 12 consecutive months) female participants only.
- i. Urine drug and cotinine (mandatory) and alcohol breath test (at discretion of the investigator) will be performed at screening from Days -28 to -2 and again on Day -1 of Period 1. These tests may be performed at any other time at the discretion of the investigator.
- j. The investigator or his/her designee will discuss with the participant the need to use highly effective contraception consistently and correctly according to contraception guidelines.

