- k. All ECG assessments will be made after at least a 5-minute rest in a supine position and prior to any blood draws or vital sign measurements. Day 4 ECGs are for Period 3 only. Single ECGs are needed for screening, times after the study intervention has been administered, Day 4 of Period 3, and upon early termination/discontinuation, while triplicate ECGs are needed for baseline.

Visit Identifier Abbreviations used in this table may be found in Appendix 10	Screening^a	Periods 1-3^b												Follow-Up	Early Termination/Discontinuation				
		Days Relative to Day 1	Days -28 to -2	Day -1	Day 1								Day 2	Day 3	Day 4	28-35 days^t			
Hours After Dose			0	0.5	1	1.5	2	2.5	3	4	6	8	12	16	24	36	48	72	

- l. Single supine BP and PR will be performed following at least a 5-minute rest in a supine position. BP and PR assessments will be performed after collection of ECGs and prior to collection of blood draws if scheduled at the same time. Day 4 measurements are for Period 3 only. Temperature will be measured as per CRU standard practice. RR will be collected if the PR is outside of normal range.
- m. Full ophthalmic exam will be conducted if treatment emergent ocular AEs are observed.
- n. See Section [8.3.6](#) for details.
- o. PF-07284890 will be administered orally on Day 1 after overnight fasting until the start of study procedures for each treatment period. PF-07284890 will be administered orally and in fasted or fed state according to the conditions described in Protocol Section [5.3.2 Meals and Dietary Restrictions](#).
- p. One (approximately 3 mL) blood sample for PK analysis of PF-07284890 will be taken at the designated time points post dose in each treatment period.
- q. Retained Research Samples Prep D1 for Genetics: If not collected on the designated collection day, collect at the next available time point when biospecimens are being collected in conjunction with a participant visit. These samples will be collected during Period 1 only.
- r. Participants will be discharged on Day 4 of of Period 3 after completion of all assessment.
- s. Collect at pre-dose for all 3 periods. For fed periods (Sequence 2 Period 1 and Sequence 1 Period 2 for the low-fat meal and Period 3 for the high-fat meal), the ECGs should be done before the pre-dose PK sample, and both should be done before the meals.
- t. Contact may occur via telephone and must occur 28 to 35 days from administration of the final dose of study intervention.
- CC1

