- v. Safety laboratories will be done on Day -1 of all 3 periods.

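### In completers, SAP 3.5.1 gives Treatment C a 28-day adverse-event window, mostly after discharge, against 5 in-house days each for A and B, so by-treatment TEAE counts are not like for like (minor)

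*SAP*

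**What the plan says.** SAP 3.5.1 first counts any event after the start of treatment as a TEAE. It then says that events in a washout or follow-up period "within the lag time of 28 days will be counted as treatment emergent and attributed to the previous treatment taken". It does not say what the 28 days are counted from.

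The calendar is in Protocol 1.3, footnotes b and c: "Period 3 will begin on Study Period 2, Day 5 (referred to as Period 3, Day -1" (bracket left open here; the same applies to Period 2), and "Participants will be discharged on Day 4 of Study Period 3 following completion of all assessments". Protocol 4.1 places the high-fat meal in Period 3 for both sequences. The only scheduled contact after discharge is a telephone call 28 to 35 days after the final dose (Synopsis). Protocol 8.4.1 sets the active collection period at no less than 28 days after the last administration.

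Scheduled checks are uneven between periods (Protocol 1.3):
- Footnote k: "Day 4 ECGs are for Period 3 only".
- Footnote l, on vital signs: "Day 4 measurements are for Period 3 only".
- Footnote f: "A brief PE will be performed on Day -1 of Periods 2 and 3".
- Footnote v: "Safety laboratories will be done on Day -1 of all 3 periods".
- Footnote s, on predose ECGs, vital signs and PK: "Collect at pre-dose for all 3 periods".

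SAP 6.5.1 leaves AE reporting to the sponsor's CaPS standards and states a by-treatment presentation only for discontinuations due to AEs. SAP section 4 analyses the safety set by product received. SAP 3.5.1, 6.5 and 6.5.1 give no common window, no adjustment for observation time and no split between in-house and later events.

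**The concern.** The attribution rule exists to assign events to treatments. For A and B, the next dose cuts the lag short. For C there is no next dose, so the lag runs in full. Because C is last in both sequences, randomisation cannot even this out.

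The windows also differ in how events are found. Those for A and B lie wholly inside the unit. Most of the C window is outpatient time that rests on one call. In-house, the Day 4 ECG and vital signs follow C only, while the Day 5 laboratory tests and brief examination, and the next period's predose checks, follow A or B only.

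Safety and tolerability is a secondary objective, and Protocol 4.2.1 expects the high-fat meal might raise exposure by up to about 2-fold. A reader will therefore look at the C column of a TEAE table for a signal. A difference there could reflect window length and follow-up rather than the meal, and with about 12 participants a few follow-up events could dominate that column.

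**Working it through.** **1. Reproduce the plan's calendar.** Set Period 1 Day 1 = 0 and Day -1 = -1. Day 5 of a period is Day -1 of the next, so doses fall at 0, 5 and 10 (study Days 1, 6 and 11). Discharge on Period 3 Day 4 is at 10 + 3 = 13. The stay is 13 - (-1) + 1 = 15 days and 14 nights, and doses are 5 days apart. Both match the protocol.

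**2. Attribution windows in completers.** A window runs from a dose to the next dose, or to the end of the lag if there is none. The lag is taken from the dose (an assumption, in line with Protocol 8.4.1).
- A: 5 days, all in-house.
- B: 5 days, all in-house.
- C: 28 days = 3 in-house + 25 after discharge.
- Ratio: 28/5 = 5.6. If the lag ran from Period 3 Day 4, the C window would be 3 + 28 = 31 days and the ratio 31/5 = 6.2.

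**3. Person-days with 12 completers.** A is 12 x 5 = 60, B is 60 and C is 12 x 28 = 336 (36 in-house, 300 after discharge). The total is 456, of which C has 336/456 = 73.7%.

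**4. What this does to counts when there is no true difference.** Assume a constant background AE rate, and let f be capture after discharge relative to capture in-house. Neither is in the documents. The expected C:A count ratio is (3 + 25f)/5.

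| f | C:A |
|---|---|
| 0 | 0.60 |
| 0.08 | 1.00 |
| 0.10 | 1.10 |
| 0.25 | 1.85 |
| 0.50 | 3.10 |
| 1.00 | 5.60 |

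The ratio passes 1 at f = 2/25 = 0.08. Above that the artefact inflates C; below it, C is understated.

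**5. Days 29 to 35.** If the first sentence of SAP 3.5.1 governs, events up to a day-35 call also count. The C window is then up to 35 days: 35/5 = 7.0 times A or B, and 420/540 = 77.8% of the total.

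**6. Effect of a split at the Day 4 (nominal 72 h) assessments.**

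| Person-days, 12 completers | A | B | C |
|---|---|---|---|
| Dose through Day 4 | 36 | 36 | 36 |
| Later | 24 | 24 | 300 |

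Observation time in the first row is equal. The later row holds 348/456 = 76.3% of the total. Ascertainment is not equalised: if the Day 4 ECG and vital signs add a fraction s of events after C, the first-row count ratio is 1 + s (1.10 at s = 0.10, 1.25 at s = 0.25; s is not in the documents).

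**The case against.** The strongest reply is that no planned comparison is harmed. No hypothesis is tested, the safety objective names no contrast between meals, and the TEAE table layout sits in CaPS, which is not available and might already handle this. That stands as a limit on severity. It does not remove the point: the rule is stated in the SAP, any summary by attributed treatment inherits it, and the SAP states no adjustment.

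A second reply is that attribution to the last treatment, with follow-up of at least 28 days, is a conservative safety convention. The investigator also judges causality for each event, taking timing into account, and with half-lives of 5.7 to 10 hours (Protocol 4.2) most of the drug is gone by discharge. This is fair, and it is why the rule should stay. But a causality judgement on single events does not correct all-causality counts by treatment.

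Third, a cut at exactly 72 hours would land on the Period 3 Day 4 assessments, with no rule for results just either side. That is right, so the boundary should be the scheduled assessments themselves, included. One might also wish to flag events found only by the unmatched checks, but the AE recording sections describe no field for the detecting assessment, so no flag is asked for.

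Fourth, the second sentence of SAP 3.5.1 can be read as qualifying the first. That is reasonable; what remains on days 29 to 35 needs only a clarifying clause.

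A reader might also infer that the rule makes the high-fat meal look less safe. The documents do not support this, because the ratio may fall on either side of 1 (working, step 4).

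**Conclusion.** The point holds and is minor. In participants dosed in all three periods, TEAE counts by attributed treatment rest on windows of 5, 5 and 28 days (60, 60 and 336 person-days with 12 completers) that also differ in ascertainment. The 5.6-fold figure is a ratio of window lengths, not an estimate of bias in counts.

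It assumes the planned 5-day schedule and a lag counted from the dose. A participant who stops after A or B would carry the lag on that treatment instead, and a delayed Period 3 would lengthen the window of the Period 2 treatment.

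Two stronger conclusions are not supported. The first is that the food-effect results or the decision to start Period 3 are compromised: the PK ratios do not use AE attribution, the pre-Period 3 review uses data from Periods 1 and 2, and A versus B in completers has equal windows. The second is that a common window would make C fully comparable: C stays confounded with period, and its in-house checks differ from those after A and B.

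**What to change.** In SAP 3.5.1 and 6.5.1, keep the attribution rule and the all-events total, and add the following.
- In any by-treatment TEAE table, show events from dosing through the scheduled Day 4 (nominal 72 h) assessments of each period, with those assessments included, separately from later events. Later events run from that point to the next dose or, after the last dose, through follow-up, labelled by the last treatment taken.
- Read treatments side by side only on the common-window columns.
- Footnote the window lengths. State that the split equalises time only, because Day 4 ECGs and vital signs are in Period 3 only, while Day 5 laboratory tests and brief examinations and the next period's predose checks follow Periods 1 and 2 only.
- As a minor clarification, state what the 28-day lag is counted from and how events on days 29 to 35 are classified.

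The cost is SAP wording, one or two table columns and a footnote. No event is dropped and no new data are needed. The real downside is fewer events in the like-for-like columns: about 76% of attributed person-days move to the later columns, including the Day 5 findings after A and B.
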